 - Although this condition is termed “mandatory” use, it is not a hard stop. The provider can easily close the window without consulting the PDMP and the prescription can be signed whether the PDMP has been consulted or not. The BPA will be built to track utilization of the BPA vs. bypass. Note: This has been deemed too interruptive for

[figure not shown]

Figure 2: Example BPA used in prior study.

ambulatory clinics and they will not be included in this arm.

3. Arm 3: CDS for high risk patients based on PDMP data
 - Based on initial interviews with providers (see 19-3063) CDS support will be designed to be supportive of provider workflows via interruptive alerts (BPAs) for high-risk patients only. No alerts will fire for patients without high risk indicators based on data in the PDMP or prescription history as shown in Epic. An example is given below. Exact phrasing may be modified during final testing in order to streamline appearance of the alert.
 - Again, BPA will be triggered upon entry of an opioid or benzodiazepine prescription and will fire only for patients determined to be at risk for controlled medication associated adverse events, misuse or overdose, based on logic built to identify high-risk characteristics. Definition of these risk characteristics is based on CDC guidelines and include: NarxCare opioid or overall overdose risk score (PDMP based) indicating the patient is in the highest ~5% of the population for controlled medication risk, initiating opioid treatment with an extended or long acting release formulation with no opioid usage in the previous 100 days, or information in the PDMP or EHR indicating overlapping opioid use or co-prescribing of a sedative with an opioid.
 - One-click access to the PDMP for all patients will be maintained as in other arms. If the provider reviews the PDMP during the encounter before prescribing, the BPA will be suppressed.

- As in Group 2, this is not a truly mandatory check and can be bypassed. BPA messaging was determined based on work with providers to deliver the most useful and clear information.
- The text displayed in the alert will be specific to the patient. BPA logic and phrasing is included in Appendix A.

[figure not shown]

Figure 3: Sample alert.

4. Arm 4: CDS for high risk patients based on PDMP and/or clinical characteristics

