- The CDS will fire based on the same characteristics as in Group 3 OR if clinical history characteristics recorded in the EHR indicate increased high-risk. Again, these risk factors have been determined based on work with providers and include risk factors based on prior published work[9; 10]. Factors included are: history of overdose, an active mental health diagnosis, a history of positive tox screen for illicit drugs, an active or prior diagnosis of a substance use disorder, or multiple recent ED visits which included administration of an opioid.
- One-click access to the PDMP for all patients will be available as in other arms. If the EHR encounter includes records of a PDMP check, the BPA will be suppressed and not fire.
- As in Group 2 and 3, this is not a truly mandatory check and can be bypassed.

The exact messaging included in and format of the BPAs were determined based on the results of study 19-3063 and technical feasibility. For high-risk prescribing, each BPA will provide an alert and embedded link to action (“check the PDMP”), a reason (“your patient is at high risk due to XXX”) and a link to a website providing more information about the study, the logic used to fire the CDS and resources for prescribers such as the CDC Guidelines. No treatment recommendations will be made as the goal of the CDS is to encourage providers to make effective use of existing resources to inform their prescribing. BPAs will be designed to track provider use vs. bypass.

A series of silent alerts will be used to capture information about patient risks and provider PDMP usage over time. For Arms 2 and 3 as described above, an alert nearly identical to the study alert will fire but not be visible to the provider (2nd level in model). The silent alert will have the same PDMP and EHR criteria but will not filter out patients for whom the provider has already checked the PDMP (suppressed in provider alert). This will allow tracking of provider PDMP behavior change over time since we will have PDMP use due to BPA and PDMP by provider which suppresses BPAs. This is important to identify behavior change regarding PDMP use by providers.

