Activation of the alert will be monitored using automated tracking within Epic which identifies providers and patients associated with alert firings. A key feature of the CDS is that the PDMP check must be "attested" to in order to suppress the CDS and prevent re-firing of the alerts, which is interruptive to the provider. This attestation is a workflow change for providers and is essential for CDS success. It can happen prior to prescription entry, in which case the alerts will not activate (suppression), or after activation of the alert.

In the event that providers are being "hit" with CDS alerts multiple times within the same encounter for a single patient because they miss the attestation step, an educational message with a link to the education website will be sent to the provider via email or EHR internal messaging systems to remind the provider to click the attestation button in order to prevent multiple firings. A weekly tally of messages sent will be retained, but no patient information will be retained. No provider will receive more than three educational reminders. The reminder will not include any patient information. This check is intended only to provide an additional personalized education step.

This is important because (1) dissemination of education about new CDS across all of UCHealth is challenging so we will miss providers and (2) we have concerns that if providers find the CDS to be a nuisance (due to a simple knowledge gap of not understanding the attestation requirement) they will not use the CDS.

Similarly, if a provider receives multiple alerts but does not access the PDMP in response, a reminder will be sent that checking the PDMP requires the same number of "clicks" as dismissing the alert and is considered best practice prior to prescribing. As with the contact

described above, these reminders will not contain any patient specific information and are designed as a personalized education step. No provider will receive more than three contacts in this way.

From initiation of educational messages until 9/20/2021, providers who receive one of the above educational messages will receive the message via email. Educational messages sent on or after 9/21/2021 will be sent via internal messaging within the EHR. This change in educational message delivery will allow for examination of best practices with providers.

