3. Description of use of the PDMP and study-associated BPAs, specifically monitoring
 - # of times PDMP activity/website is checked by site/practice/service, monthly, and specialty
 - Frequency of use of the PDMP one-click button per visit and per opioid prescription
 - Frequency of CDS and BPA trigger overall and per opioid prescription
 - Frequency of prescriptions for which the BPA would have fired but the prescriber had already checked the PDMP (look for change over time – do the BPAs lead to learning & change in prescriber behavior)
 - Number of times CDS alert fired, total and per visit (the alert is designed to only fire once during any encounter, thus the per visit rate will be <1)
 - Reviewed (via radio button or via alert)/unable to review/blank

- Resulted in signed Rx (reviewed/unable checked, signed prescription)
- Use of training tools and website. Identifying information on individuals accessing tools will not be recorded.
- Qualitative/semi-quantitative feedback from users as the CDS alerts are implemented

Patient specific measures will include:

- Number of controlled medication prescriptions, both within UCHealth and outside, based on PDMP data (including prescription details to include generic name, dosage, MMEs, days prescribed)
- Use of the PDMP by the prescriber prior to each controlled medication prescription written
- NarxCare risk score at the time of each prescription
- Number of providers/practices used for controlled substance prescriptions
- Number of pharmacies used for controlled substance prescriptions
- Diagnosis of any substance use disorder after the index visit date
- Accidental overdose of controlled substance after the index date (if data available)
- Patient demographics and clinical history characteristics

Educational outreach analysis: Alert firings for providers part of the educational outreach group will be analyzed for percent of non-compliant firings before outreach vs after as well as a comparison between the two different educational outreach efforts (email or EHR messaging system). Non-compliance is defined as 3 or more alerts for a single patient/encounter or >80% of firings closed using the comment/close option rather than using the PDMP link. Firings over time will be tracked as will changes in compliance before and after each outreach attempt. These data will be de-identified prior to reporting. Data will be examined for patterns based on demographics or work environment.

Calculation of sample size:

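### The outreach measure counts only alerts that fired, so it gives no credit to providers who learn to check the PDMP first and can understate the benefit of the messages

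*Combined protocol and SAP*

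**What the plan says.** Section IV.F (Educational outreach analysis) sets the outcome: "Alert firings for providers part of the educational outreach group will be analyzed for percent of non-compliant firings before outreach vs after". It adds a comparison of the email and EHR-message channels. "Non-compliance is defined as 3 or more alerts for a single patient/encounter or >80% of firings closed using the comment/close option" without going to the PDMP link. Both limbs can be scored only on a visible alert that fired. The paragraph also promises to track firings over time and compliance around each outreach attempt. It names no test, no model and no denominator of eligible orders.

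Section IV.C, on attestation of the PDMP check: "It can happen prior to prescription entry, in which case the alerts will not activate (suppression), or after activation of the alert". The Arm 3 description says the same: "If the provider reviews the PDMP during the encounter before prescribing, the BPA will be suppressed". Arms 2 and 4 carry the same rule.

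On who is messaged, section IV.C describes one reminder for providers who miss the attestation step and so meet repeated alerts, and a second of which it says: "if a provider receives multiple alerts but does not access the PDMP in response, a reminder will be sent".

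Section IV.C and Figure 4 also describe silent alerts that a PDMP check does not suppress. The second-level mirror in Arms 2 and 3 "will not filter out patients for whom the provider has already checked the PDMP", and a third-level silent alert runs in every arm.

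**The concern.** A qualifying order can end in one of three ways: the PDMP is checked first and nothing fires; an alert fires and leads to a PDMP review; or an alert fires and is closed without review. The planned percentage sees only the last two. A provider who moves to the first stops contributing firings, and the later firings come increasingly from providers who did not change.

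Checking first is a real form of success. The hospital system measures in section IV.F list orders where the alert would have fired but the PDMP had already been checked, and treat a rise in them as learning. That measure is not linked to the outreach comparison.

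At stake is whether the messages are judged to work and which channel is preferred. Section IV.C says the switch of channel is meant to inform best practice. A channel that prompts more checking first gains nothing for it on this measure.

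**Working it through.** The plan gives no expected percentage, response rate or sample size for this analysis, so there is no figure to reproduce. All inputs below are assumptions. Closing rates are set just above the plan's 80% threshold, and non-compliance is first scored as the closed share of firings.

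**Notation.** For a group with weight w, q is the share of qualifying orders checked first and c the share of fired alerts closed without review.
- Fired: F = Σ w(1 − q)
- Closed: C = Σ w(1 − q)c
- Planned measure: M = C/F
- Unchecked share of all qualifying orders: U = C

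**1. Responders only check first.** Half respond; their q goes from 0.10 to 0.70; c = 0.85 for everyone.
- Before: F = 0.90, C = 0.90 × 0.85 = 0.765. M = 85.0%, U = 76.5%.
- After: F = 0.5 × 0.30 + 0.5 × 0.90 = 0.60, C = 0.60 × 0.85 = 0.51. M = 85.0%, U = 51.0%.

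**2. As 1, but responders close 82% and non-responders 95%.**
- Before: M = (0.82 + 0.95)/2 = 88.5%, U = 0.90 × 0.885 = 79.65%.
- After: C = 0.15 × 0.82 + 0.45 × 0.95 = 0.5505. M = 0.5505/0.60 = 91.75%, U = 55.05%.
- Break-even: 0.15c + 0.4275 = 0.885 × 0.60 = 0.531 gives c = 0.69. If responders' closing falls from 82% to below 69%, M improves.

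**3. As 1, but responders also close fewer alerts (85% to 50%).**
- After: C = 0.15 × 0.50 + 0.45 × 0.85 = 0.4575. M = 0.4575/0.60 = 76.25%, U = 45.75%.
- M falls by 8.75 points and U by 30.75 points, so the gain is visible but understated.

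**4. Responders use the alert's link.** Start with no checking first and c = 0.85; half respond.
- All by link: M and U both go from 85.0% to 42.5%.
- Half of responders' orders by link, half checked first: M = 0.425/0.75 = 56.7%, U = 42.5%.

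**5. Repeat-alert limb.** Suppose 60 of 100 encounters give three alerts and 40 give one. M = 180/220 = 81.8%. Half respond.
- By checking first: 90/110 = 81.8%, although encounters with repeat alerts fall from 60% to 30%.
- By attesting at the first alert: 90/(110 + 50) = 56.25%.

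**6. A per-provider summary.** A provider goes from 15 link and 85 closed to 25 checked first and 75 closed. M goes from 85/100 = 85% to 75/75 = 100%, while unreviewed orders fall from 85% to 75%. A provider who always checks first yields 0/0.

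**7. Precision, only if firings were treated as independent.** With 20 firings per provider and a nominal 5% two-sided test of email versus EHR message, the false-positive rate is 2(1 − Φ(1.96/√(1 + 19 × ICC))): 7.2%, 16.0% and 25.0% at ICC 0.01, 0.05 and 0.10.

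**The case against.** The messages, as section IV.C describes them, do not specifically ask providers to check first. One teaches attestation; the other points out that checking takes no more clicks than dismissing the alert. A provider who does what they describe, at an alert that has fired, stays in the denominator and is counted. This stands: steps 3 and 4 show the measure moving the right way once responders also change how they handle alerts. Steps 1 and 2 are the unfavourable end of the range, since they hold responders' closing rate fixed.

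A reader might infer that the plan will make a working message look useless or harmful. The documents do not support that. It needs responders who mainly check first and leave their other alert habits unchanged. Providers are also messaged because of poor response, so regression to the mean flatters the messages.

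A reader might also infer that the plan pools firings and treats them as independent. It says neither. A per-provider reading is fair, and the rates in step 7 apply only to a test the plan does not name. The denominator problem does survive that reading (step 6).

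Finally, the plan is not blind to checking first. It retains provider actions over time, and lists provider-specific PDMP use and the already-checked frequency. But none of these is tied to the outreach comparison. Firing counts alone cannot separate learning from fewer orders, and section IV.E reports a downward trend in opioid prescribing.

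**Conclusion.** The concern holds in limited form. The firing-based percentage leaves out every order checked first, so it can understate what the messages achieve. How far depends on how providers respond, which the documents do not say: on the assumed inputs, from no distortion (link only), through partial understatement (56.7% against 42.5%), to no visible change (85.0% throughout while unchecked orders fall from 76.5% to 51.0%), and to a rise where responders already closed fewer alerts than others. With regression to the mean acting in the opposite direction, the net bias has no known sign, and the planned percentage cannot by itself show whether outreach worked. The channel comparison inherits the problem only if the channels differ in how much checking first they prompt. Severity is minor to moderate: section IV.A lists outreach as neither a primary nor a secondary outcome, and the main trial comparison does not rest on it.

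**What to change.** In the outreach paragraph of section IV.F:

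- **Outcome.** Use the share of qualifying orders with no PDMP review before signing, per provider and period. Take qualifying orders from the unsuppressed silent alerts (second level in Arms 2 and 3, third level in Arm 4), and count check-first orders as compliant.
- **Review versus attestation.** Take review from recorded PDMP access where available and report attestation separately. One message teaches attestation, so better documentation alone should not be read as more checking.
- **Analysis.** Compare before and after within provider. Compare email with EHR message using a provider random effect or provider-clustered standard errors.
- **Privacy.** Work with provider-level counts by record number. Section IV.D keeps provider outreach data apart from specific patient information.
- **Description.** Keep the percent of non-compliant firings as a descriptive line.

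The cost is a wording change and one extra data link from silent-alert records to messaged providers; the silent alerts are already planned. The new outcome describes response to the visible alert less directly, which is why the firing percentage stays. It does not remove regression to the mean, so the before/after result still needs that caution.

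### The educational outreach analysis has no unmessaged comparator and splits email from EHR messages by date alone, so it cannot show whether outreach works or which channel is better

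*Combined protocol and SAP*

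**What the plan says.** **Who is messaged** (IV.C, Study Design and Research Methods). One reminder goes to providers who meet alerts "multiple times within the same encounter for a single patient because they miss the attestation step". The other covers non-use: "if a provider receives multiple alerts but does not access the PDMP in response, a reminder will be sent". Neither trigger has a numeric threshold. Each type has its own limit: "No provider will receive more than three educational reminders" and "No provider will receive more than three contacts in this way".

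**Channel** (IV.C). "From initiation of educational messages until 9/20/2021, providers who receive one of the above educational messages will receive the message via email". After that, "Educational messages sent on or after 9/21/2021 will be sent via internal messaging within the EHR".

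**Analysis** (IV.F, Educational outreach analysis). Among providers in the outreach group, the plan compares "percent of non-compliant firings before outreach vs after as well as a comparison between the two different educational outreach efforts". Non-compliance means three or more alerts in one encounter, or more than 80% of firings closed without using the PDMP link. The plan also tracks firings over time and around each attempt, and looks for patterns by demographics and work environment. It gives no before and after windows, comparator or adjustment model.

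**Purpose** (IV.C). Provider identifiers are kept so that the effectiveness of the outreach can be determined. The channel change is meant to inform best practice.

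**The concern.** Providers enter the analysis because they were recently doing badly on the measure by which they are then judged. Some of that is chance, so their later figures tend to improve without any message. IV.F also asks, among its hospital system measures, whether the alerts themselves teach prescribers to check the PDMP. That learning would fall in the after period too. Without unmessaged providers followed over the same calendar time, neither can be separated from an effect of the message.

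The channel comparison has a further problem: no date has both channels in use. Any change over time in prescribing, familiarity with the alerts or the mix of providers is carried into it. A provider may also have been emailed before receiving an EHR message, and the plan does not say how such a provider is counted.

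What is at stake is a report that outreach works, or that one channel is better, on evidence that cannot support either statement.

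**Working it through.** The plan gives no sample size, effect or error rate for this analysis, so there is no figure of its own to reproduce. The check asks how large an apparent improvement could be if the message did nothing.

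**Inputs, all assumed**
- Entry: more than 80% of *n* firings closed. This borrows the IV.F outcome definition, because IV.C says only that alerts were multiple.
- Mean close rate *m* = 1 − 0.218 = 0.782. The 0.218 is the adjusted probability of a PDMP check in section III, from an earlier ED study with a different denominator, so it is only a proxy.
- Between-provider correlation ρ from 0.05 to 0.5, and *n* = 10, 20 or 50 firings in one window. The documents give neither.
- The repeated-alert part of the definition is not modelled.

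**Formula.** Let each provider's close rate follow a beta distribution with mean *m* and *s* = 1/ρ − 1. Given *x* closures in *n* firings, the expected later rate is (*ms* + *x*)/(*s* + *n*). Averaged over selected providers whose before rate is *B*, the false drop is (*B* − *m*) × *s*/(*s* + *n*).

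**Example, *n* = 10, ρ = 0.1.** *s* = 9. Entry needs 9 or 10 closures, with beta-binomial probabilities 0.2319 and 0.1896, so 42.2% are selected (0.4215 before rounding).
- *B* = (0.2319 × 0.9 + 0.1896 × 1.0)/0.4215 = 0.945
- Drop = (0.945 − 0.782) × 9/19 = 0.077, so the rate falls from 94.5% to 86.8% with no message effect.

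**False drop in percentage points, *m* = 0.782**

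| Firings | ρ = 0.05 | 0.1 | 0.2 | 0.3 | 0.5 |
|---|---|---|---|---|---|
| 10 | 10.13 | 7.72 | 5.03 | 3.52 | 1.82 |
| 20 | 5.80 | 4.15 | 2.58 | 1.78 | 0.91 |
| 50 | 2.63 | 1.75 | 1.05 | 0.71 | 0.36 |

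Below ρ = 0.05 the drop grows further: at *n* = 10 it is 13.3 points for ρ = 0.01. It also grows with a lower mean: at *n* = 10 and ρ = 0.1 it is 13.4 points for *m* = 0.65.

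**Several periods.** I simulated six periods of 10 or 20 firings, with mean close rate 0.60 or 0.782, a provider SD of 0.65 logit, and between-period SD from 0 to 0.8 logit. The message followed the first period above 80% and had no effect.
- Averaging provider percentages equally gives a false drop of 3.1 to 11.8 points.
- Pooling firings gives between about no change and a rise of about 2 points at mean 0.782, and a drop of 1.1 to 4.8 at mean 0.60.
- With an assumed shared learning trend of −0.1 logit per period, the drop is 8.1 to 19.4 averaged and 3.0 to 11.8 pooled.

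Pooling differs because providers messaged early tend to have high close rates and supply most of the after firings. IV.F does not say which weighting applies, so size and even sign are open.

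**Channel.** Email applies to 9/20/2021 and EHR messages from 9/21/2021, so there is no overlap. IV.C activates EDs, then inpatient providers, then ambulatory practices, without dates. As an illustration only, suppose after-message close rates are 0.8 in EDs and 0.6 elsewhere, with ED shares of 0.9 in the email period and 0.5 later. The periods then differ by (0.9 × 0.8 + 0.1 × 0.6) − (0.5 × 0.8 + 0.5 × 0.6) = 0.78 − 0.70 = 8 points with no channel effect. If before-after changes were compared instead, a constant setting difference would cancel, but different stages of learning would not.

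**The case against.** The strongest reply is that this is a side analysis of a contact that the protocol plays down: "This check is intended only to provide an additional personalized education step". It is not among the outcomes in IV.A, and the plan already tracks firings over time, looks around each attempt and examines work environment. The data table in IV.F also lists provider-specific PDMP use and its change over time, not restricted to messaged providers, which could supply a concurrent comparison.

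Most of this stands, and it limits the weight of the point. It does not remove it. IV.C states effectiveness and best-practice aims, repeating before-after at each attempt repeats the selection, and nothing links the wider provider data to the outreach analysis.

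The figures are also open to challenge. The 80% entry rule is assumed, and the one-window results treat the triggering window as the whole before period. They show how the bias can arise, not how large it will be.

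Three stronger readings do not hold:
- A reader might infer that the randomised results are compromised. The IV.A outcomes do not depend on this analysis.
- A reader might take setting confounding of channel as established. Without activation dates it is only possible.
- A reader might see a contradiction between three or more alerts in an encounter and an alert designed to fire once. IV.C explains that alerts re-fire when attestation is missed, so the count captures departures from the intended behaviour.

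**Conclusion.** The point holds and is minor. As planned, the analysis can describe what happened to messaged providers. It cannot determine whether outreach was effective, or which channel is better. That conclusion is structural and rests on the text alone: entry on the judged behaviour, no unmessaged comparator, and channel set by date.

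The size cannot be determined from the documents. The range of 1.8 to 10.1 points applies only to one window of 10 firings, the assumed entry rule, mean close rate 0.782, correlation 0.5 to 0.05 and no message effect. A reader might infer that the bias always favours the message. The multi-period check does not support that: the result depends on weighting and on any learning trend, so no such range should be quoted without its weighting.

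**What to change.** 1. In IV.F, state the message entry rule, the before and after windows, and whether firings are pooled or averaged by provider.
2. Estimate the outreach effect against concurrent unmessaged providers who see alerts (Arms 2 to 4; Arm 1 sees none), using the provider-level firings already tracked in Epic. Include a message term that starts at the message date, terms for time since activation, setting and study arm, and a provider effect. State that bias remains if a provider's behaviour varies from period to period, because the provider effect removes only stable differences.
3. Label the plain before-after table and the email versus EHR comparison descriptive. Report the latter by setting and outreach attempt, and draw no effectiveness or best-practice conclusion from either.

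The cost is a short change to the analysis plan and one provider-level model. Setting and message method are already retained. Unmessaged providers would need de-identified record numbers of the kind described in IV.D. The price is a wider interval and a less definite conclusion about outreach.

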In our prior work at UCHealth EDs, we sought to reduce barriers to PDMP use and investigate the effectiveness of improved access to the PDMP and "mandated" consultation of the PDMP prior to signing an opioid e-prescription. We determined PDMP usage rates, prescription rates when the PDMP is used (or not), and patient outcomes. In the setting of already decreasing opioid prescribing, we found that one-click PMDP EHR integration is associated with an increase in the frequency of PDMP searches for ED patients who are prescribed an opioid. Unfortunately, still only a minority of ED patients receiving an opioid prescription were searched even after mandating use through an interruptive "best practice alert". "Mandated" use for our studies, is a relatively loose term. In order to not disrupt clinical workflows, information is presented as a "best practice alert" (BPA) in a pop-up window but providers can act on or bypass the alert. This design is required in order to ensure the tool does not impede patient care or the exercise of clinical judgment. Additionally, use across different ED sites and providers was highly variable, suggesting inconsistent care and the need for improvement.

After adjusting for site, provider and the patient's race/ethnicity and age, the predicted probability that a patient who received an opioid prescription would have been checked in the PDMP was only 0.218 (95% CI: 0.202 – 0.234) under the most stringent "mandatory" use criteria in our previous study.

Notably, there was a significant reduction in the probability that an opioid was prescribed as the number of opioids filled in the six months prior to the ED visit increased if the patient was searched in the PDMP (OR: 0.92 [95%CI:0.91-0.94] for every additional prescription). There was no such reduction for patients who were not searched (OR: 1.01 [95%CI:1.00-1.01] for every additional prescription). This suggests that reviewing the PDMP did have an effect on prescribing behaviors for high-risk patients.

We conclude that providing effective information on prior controlled medication use and risk assessment improves patient safety by decreasing high-risk prescribing. However, given poor compliance with "mandatory" consultation of the PDMP, it is clear that improvements are needed in information presentation to facilitate PDMP use. To address this

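### The outreach outcome is a percent of non-compliant firings, but the >80% limb that defines non-compliance is a share over many firings, with no minimum count or time window

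*Combined protocol and SAP*

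**What the plan says.** Section IV.F, educational outreach analysis, says that alert firings of providers in the outreach group "will be analyzed for percent of non-compliant firings before outreach vs after". Its definition has two limbs: "Non-compliance is defined as 3 or more alerts for a single patient/encounter or >80% of firings closed using the comment/close option", as opposed to following the PDMP link. It gives no minimum number of firings, no period over which the share is taken, and no rule for combining the limbs into one percentage. Changes in compliance are also to be followed around each outreach attempt.

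Section IV.C describes two kinds of reminder. One goes to providers who are alerted repeatedly in an encounter because they missed the attestation step. The other is sent "if a provider receives multiple alerts but does not access the PDMP in response". For this second kind, "No provider will receive more than three contacts in this way". The word for the number of alerts is not quantified.

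The hospital system measures in section IV.F describe the alert as built to fire a single time in an encounter, giving a rate below 1 per visit.

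**The concern.** A percent of non-compliant firings needs a yes/no label on every firing. A provider's overall share of closed alerts does not supply one. Two analysts could follow the text faithfully and report different percentages from the same data.

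The limbs also measure different things. By section IV.C, repeat firing in one encounter reflects a missed attestation, so a prescriber who did look at the PDMP can be caught by it. The >80% limb concerns not using the PDMP link. A pooled percentage would not show which behaviour had changed.

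Finally, a raw share on few firings is noisy. If high shares select prescribers for outreach, a before/after comparison is biased towards showing that the message worked.

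**Working it through.** **1. Is the outcome defined?** Take a provider with 100 firings before and 100 after, one per encounter, of which 81 and then 79 are closed.

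| Reading of a non-compliant firing | Before | After | Change |
|---|---|---|---|
| Any closed firing | 81% | 79% | −2 points |
| Closed firings of a provider above 80% | 81% | 0% | −81 points |
| All firings of a provider above 80% | 100% | 0% | −100 points |

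The text does not choose between these. The 3-alert limb can mark the firings of one encounter, so the gap lies in the >80% limb and in joining the two.

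**2. Do the passages agree on repeat firing?** The outreach definition needs three or more alerts in an encounter, and section IV.C expects re-firing when attestation is missed. The system measures say the alert fires once per encounter. These passages must be reconciled.

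**3. Chance labelling at low counts.** Let p be the true probability that a firing is closed and n the number of firings. The provider is labelled if X/n > 0.80, with X binomial(n, p). For n ≤ 5 every firing must be closed, since 4/5 is exactly 80%, so the probability is pⁿ. For p = 0.5: 0.5¹ = 50%, 0.5² = 25%, 0.5³ = 12.5%. The values of p are assumptions, because the documents give no close rate.

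| n | closed firings needed | p = 0.5 | p = 0.6 | p = 0.7 |
|---|---|---|---|---|
| 2 | 2 | 25% | 36% | 49% |
| 3 | 3 | 12.5% | 22% | 34% |
| 5 | 5 | 3% | 8% | 17% |
| 6 | 5 | 11% | 23% | 42% |
| 10 | 9 | 1% | 5% | 15% |
| 20 | 17 | 0.1% | 2% | 11% |

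The chance stays at or below 5% only beyond 7 firings (p = 0.5), 16 (p = 0.6) or 56 (p = 0.7).

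**4. Fall with no real change.** Suppose prescribers enter the before/after comparison because their raw share exceeded 80%, and the same firings supply the before rate. For n ≤ 5 that rate is 100% by construction, while the expected after rate is the prescriber's true rate.

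To illustrate larger n, take a constant close rate of 0.782, the complement of the prior study's 0.218 (section III), on the assumption that a non-check equals a closed alert. The mean of X/n given X/n > 0.80 is 93% at n = 10 and 88% at n = 20, with 78% expected after. The spurious falls are about 14 and 10 points.

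A constant rate is the extreme case, since section III reports that "use across different ED sites and providers was highly variable". Let true rates follow a beta distribution with mean 0.782 and intraclass correlation ρ, assumed 0.05 to 0.30. Then a = 0.782(1−ρ)/ρ, b = 0.218(1−ρ)/ρ, and the expected after rate given x closed is (a + x)/(a + b + n).
- n = 2, ρ = 0.05: (14.858 + 2)/(19 + 2) = 80%, against 100% before.
- n = 2, ρ = 0.30: (1.825 + 2)/(2.333 + 2) = 88%, against 100% before.
- n = 10, averaged over x = 9 and 10: 94% before and 84% after at ρ = 0.05; 97% before and 93% after at ρ = 0.30.

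So the artefact is about 12 to 20 points at 2 firings and 3 to 10 points at 10 firings when providers vary.

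**The case against.** The best defence is that the data suffice and only the wording is loose. Whether a firing was closed or led to the PDMP link is tracked per firing, so a close share is computable for each provider. That is true, and it makes the fix cheap. It does not tell the analyst which percentage the plan intends.

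Three stronger readings are tempting, and the documents do not support them.

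- **The limit sits at the prior average and so labels many ordinary prescribers.** Section III says that a patient given an opioid prescription "would have been checked in the PDMP was only 0.218 (95% CI: 0.202 – 0.234) under the most stringent" criteria, so 78.2% were unchecked (76.6% to 79.8%). That is near 80% but below it, and it is another quantity: an adjusted probability for ED patients given an opioid, under an earlier alert. The limit counts visible alerts that were closed. Alerts are suppressed where the PDMP was already reviewed, are restricted to high-risk patients in Arms 3 and 4, and extend to inpatient and ambulatory care. Suppression could raise the closed share and targeting could lower it. Section III also treats the earlier compliance as poor, so a prescriber at that level is arguably an intended target.
- **One closed alert triggers a message.** One of one is 100% and meets the >80% limb as written, but the reminder in section IV.C requires more than one alert.
- **Most labels are wrong.** Under the beta model above, about 72% to 93% of providers labelled at 10 firings truly close more than 80%. At 2 firings it is about 56% to 79%. The problem is concentrated at low counts.

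The comparison of email with EHR messaging is less exposed to regression to the mean, provided both groups were selected by the same rule on similar numbers of firings.

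**Conclusion.** The point holds for the educational outreach analysis. The >80% limb cannot label a firing, is not joined to the 3-alert limb, and has no minimum count or window. The once-per-encounter statement conflicts with the 3-alert limb. The definitional gap needs no assumption.

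The chance-labelling figures rest on assumed close rates and independent firings. The regression figures assume that a high raw share selects prescribers and that the same firings form the before rate. Section IV.C gives no number for its trigger, so the plan neither confirms nor excludes this. Their size also depends on the unknown spread between providers. The 0.782 rate serves only as an illustration.

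The importance is low. The consequences are a limited number of educational reminders and a side analysis, and neither the primary nor a listed secondary outcome depends on the definition.

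**What to change.** - **Outcome.** Analyse one binary result per alerted encounter: alert closed or order signed with no PDMP review recorded, versus reviewed. State how an unable-to-review entry is handled. Fit a model with a provider random effect. The plan already captures review status and whether a prescription was signed, and section IV.E already foresees random effects for provider-level outcomes.
- **Repeat firings.** Report three or more firings per encounter as a separate outcome, so that missed attestation stays visible, and reconcile it with the once-per-encounter statement.
- **The >80% rule.** Keep it only as a provider-level outreach classification, with a stated minimum number of alerted encounters and a stated time window. A minimum removes the worst chance labelling but cannot separate prescribers whose true rate is close to 80%. Classifying on a shrunken model-based rate is an option, not a requirement.
- **Before rate.** Exclude the firings that triggered the outreach, or account for regression to the mean in another stated way.

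The cost is a change of wording in section IV.F and a small change to the monitoring report. Some low-volume prescribers will not be classified.
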